## 10.2 Plans for Expansion at the MTD

Once the MTD has been defined, 10 additional patients will be enrolled, to provide preliminary efficacy data. One month of observation after SRT will not be required between groups of patients during the expansion phase, but monitoring DLT will be performed, as described in the next section.

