## 9.3 Data and Safety Monitoring Plan

This protocol will comply with monitoring and adverse event reporting requirements of the UNMC/Eppley Cancer Center Data Monitoring Plan. All research data will be stored in the case report forms in a locked file cabinet. These forms are available only to the investigators, his/her designee (i.e., the study coordinator), the UNMC Eppley Cancer Center Scientific Review Committee (SRC), and representatives of the Institutional Review Board at the University of Nebraska Medical Center. Any information obtained during this study which could identify the subject will be kept strictly confidential and will be identified by code numbers rather than the patient's name. The data safety plan also includes: Weekly review of all patients on study by the investigators. All adverse events will be reported to the PRMS Internal Audit Committee for audit by a clinician not involved with the clinical trial.

All patients will be closely followed for toxicity. Toxicity will be assessed using the revised NCI Common Toxicity Criteria (version 3.0) retrieved from the National Cancer Institute, Cancer Therapy Evaluation Program web site: ([ctepcancer.gov/forms/CTCAEv3.pdf](http://ctepcancer.gov/forms/CTCAEv3.pdf)). Therapy will be discontinued at any time due to the development of unacceptable toxicity. If a Grade 1 or 2 or 3 toxicity develops, the investigator may elect to continue the treatment with careful monitoring. Any grade 4 or greater toxicity according to CTCAE v3 will constitute a DLT. 1) SRT dose escalation will be stopped if 2 patients at a given dose level experience a DLT. If one patient has a DLT, then an additional five patients will be evaluated at the same dose level. 2) Implantation of a liver marker will be stopped if 2 patients experience implant-related-adverse events which do not response to medical or surgical management.

Therapy will be discontinued at any time due to the development of unacceptable toxicity. If, at any time, the data suggest a significant hazard to further dose escalation, regardless of whether the formal stopping rules are satisfied, dose escalation will be halted pending a review of all data. There will be a four week waiting period after the last patient in each cohort completes radiation therapy for toxicity evaluation between dose levels.

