#### Endpoints

Toxicity will be graded by NCI Common Toxicity Criteria (CTC Version 3.0). Due to delayed toxicities attributable to radiotherapy, all toxicities observed within 1 month after SRT will be scored. DLT is defined as any of following toxicities, that is possibly, probably or definitely related to SRT occurring within 30 days from the start of treatment:

- a) grade 4 or 5 hepatic
- b) grade 4 or 5 gastrointestinal
- c) grade 4 or 5 thrombocytopenia
- d) grade 4 hepatic liver enzyme elevations persisting for  $\geq 5$  days
- e) any adverse event requiring interruption of therapy by  $\geq 2$  weeks (14 calendar days). This does not include patient desire to discontinue therapy. It does include failure for thrombocytopenia to improve to a level of 80 requiring interruption of therapy.
- f) Any grade 5 treatment-related adverse event

The MTD of SRT is defined as the highest dose level at which no greater than 2 DLT is observed in 6 patients.

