#### Dose-escalation Rules

A standard cohort escalation design will be employed to evaluate 3 dose levels of SRT. Three patients will initially be treated at each dose level. A minimum of 1 month of observation after surgery is required in all 3 patients before escalation is initiated.

At the second dose level, 3 patients are entered. If:

0/3 have DLT	then the third dose level is investigated.
2/3 have DLT	then the MTD is exceeded at the second dose level. De-escalation of SRT to the first dose level will be considered.
1/3 have DLT	then 3 additional patients are entered. If none of the additional patients develop DLT, then the third dose will be investigated. Otherwise, the MTD is exceeded at the second dose level. De-escalation of SRT will be considered.

At the third dose level, 3 patients are entered. If:

0/3 have DLT	then the fourth dose level is investigated.
2/3 have DLT	then the MTD is exceeded at the third dose level. The second dose level will be expanded to a total of 6 patients (if only 3 patients had been treated).
1/3 have DLT	then 3 additional patients are entered. If none of the additional patients develop DLT, then the fourth dose will be investigated. Otherwise, the MTD is exceeded at the third dose level.

At the fourth dose level, 3 patients are entered. If:

0-1/3 have DLT	then 3 additional patients are entered. If at most 1 of 6 patients develops DLT, then the fourth dose will be declared the MTD. Otherwise, the MTD is exceeded and the third dose level will be expanded to a total of 6 patients (if only 3 patients had been treated).
2/3 have DLT	then the MTD is exceeded and the third dose level will be expanded to a total of 6 patients (if only 3 patients had been treated).

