## 10.3 Monitoring Dose-Limiting Toxicity

With 6 evaluable patients, the probability of not escalating when the true DLT rate is 35% or higher is at least 68%. If the true DLT rate is 20%, the probability that the dose will be escalated is 66%.

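### Section 10.2 waives the observation month for the 10 expansion patients and points to 10.3 for DLT monitoring, but 10.3 contains no rule that could pause accrual at the MTD

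*Combined protocol and SAP*

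**What the plan says.** Section 10.2 sets the size and purpose of the expansion: "Once the MTD has been defined, 10 additional patients will be enrolled, to provide preliminary efficacy data". Section 10.1 adds that the same patients serve to evaluate toxicity further. Section 10.2 then removes the staging between groups, "One month of observation after SRT will not be required between groups of patients during the expansion phase", and offers one safeguard in its place: "monitoring DLT will be performed, as described in the next section".

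The next section is 10.3, headed as the section on monitoring DLT. It consists of two sentences:

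- "With 6 evaluable patients, the probability of not escalating when the true DLT rate is 35% or higher is at least 68" per cent.
- "If the true DLT rate is 20%, the probability that the dose will be escalated is 66" per cent.

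Section 10.4 says that toxicity will be tabulated by dose level.

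Outside Section 10, the only numeric rule for SRT toxicity is in 9.3: "SRT dose escalation will be stopped if 2 patients at a given dose level experience a DLT". The discretionary clause in 9.3 also halts dose escalation, and its four-week wait applies between dose levels.

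The result that qualifies a dose as the MTD is stated in two ways. Under Endpoints in 10.1: "The MTD of SRT is defined as the highest dose level at which no greater than 2 DLT is observed in 6 patients". Under Dose-escalation Rules, the fourth level is declared the MTD only if at most 1 of 6 patients has a DLT.

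**The concern.** The promise in 10.2 cannot be carried out as written, because the text it points to has no DLT count, look schedule, threshold or action for the expansion. The rules in 9.3 do not fill the gap: they stop or halt escalation, and once the MTD is fixed there is no escalation left to stop.

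A dose that has passed on about six patients is only weakly established, and the expansion is where an unsafe choice would show. The DLTs listed in 10.1 include grade 4 or 5 hepatic and gastrointestinal events and treatment-related deaths. With the observation interval waived, several patients can be treated before earlier ones have finished the 30-day DLT window.

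**Working it through.** **1. What the figures in 10.3 describe.** Inputs from 10.3: 6 patients, true DLT rates of 35% and 20%. Assume a fixed group of 6, with escalation if at most 1 has a DLT.

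- Not escalating at 35%: 1 − [0.65^6 + 6(0.35)(0.65^5)] = 1 − (0.0754 + 0.2437) = 0.681. Stated: at least 68%.
- Escalating at 20%: 0.8^6 + 6(0.2)(0.8^5) = 0.2621 + 0.3932 = 0.655. Stated: 66%.

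Both figures reproduce, so 10.3 concerns an escalation decision on 6 patients and not an expansion of 10. As a side point, the sequential rule under Dose-escalation Rules, (1−p)^3 + 3p(1−p)^2(1−p)^3, gives 60.4% not escalating at 35% and 70.9% escalating at 20%. That mismatch is a separate matter and nothing below depends on it.

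**2. How easily a 35% dose looks acceptable in 6 patients.**

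- At most 1 of 6: 0.0754 + 0.2437 = 0.319, or 32%.
- At most 2 of 6: 0.319 + 15(0.35^2)(0.65^4) = 0.319 + 0.328 = 0.647, or 65%.

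These are chances of passing at one dose level, not the chance that the whole trial selects that dose.

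**3. What 10 expansion patients would show.** Binomial with n = 10. At 35%, P(at most 3) = 0.0135 + 0.0725 + 0.1757 + 0.2522 = 0.514, so P(4 or more) = 0.486.

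| True DLT rate | Expected DLTs in 10 | P(4 or more) |
|---|---|---|
| 20% | 2.0 | 12% |
| 35% | 3.5 | 49% |
| 50% | 5.0 | 83% |

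With no boundary, the chance of a rule-based pause is zero at every rate.

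**4. What a boundary could do (illustration only).** These limits are an assumption and are not in the documents: count all DLTs at the MTD over 6 + 10 = 16 patients, and pause at 3 in up to 9 patients, 4 in 10–12, or 5 in 13–16. The starting count for the first 6 follows the binomial, restricted to at most 1 or at most 2 DLTs. Each further patient adds a DLT with probability p, and a path ends when it reaches the limit. Each outcome is taken as known before the next patient enters. A crossing at patient 16 spares nobody, so the relevant column stops at patient 15.

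| First 6 at the MTD | True rate | Crosses by patient 15 | Crosses by patient 16 |
|---|---|---|---|
| At most 1 DLT | 20% | 12% | 13% |
| | 35% | 43% | 50% |
| | 50% | 77% | 83% |
| At most 2 DLTs | 20% | 24% | 26% |
| | 35% | 64% | 68% |
| | 50% | 90% | 93% |

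**The case against.** The strongest reply is that the expansion is not unmonitored, and that is correct. Section 9.3 provides weekly review of all patients by the investigators, audit of adverse events by a clinician outside the trial, and discontinuation of therapy for unacceptable toxicity. Section 9.2 sends adverse event reports to the DSMC, and 5.6.3 removes a patient who has a DLT. A reader might infer that 10 patients are treated with no safety oversight. The documents do not support that. What they lack is a prespecified count at which accrual pauses.

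A second reply is that the 2-DLT rule in 9.3 was meant to cover any dose level, including the MTD. Its reference to a given dose level makes this a possible intention, but its stated action is to stop escalation. It does not say whether DLTs from the escalation phase count, and under the Endpoints definition an MTD could already have 2 DLTs before the expansion starts. Applied to the expansion patients alone, a limit of 2 would be met 62% of the time at a true rate of 20%: 1 − 0.8^10 − 10(0.2)(0.8^9) = 0.624.

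A third reply is that a small expansion can reasonably run without a formal boundary. As a design choice that is arguable, but this plan says that monitoring is described and then does not describe it.

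Finally, a boundary would spare fewer patients than the table suggests when several are in their 30-day windows at once. This stands, and the fix has to address it.

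**Conclusion.** The point holds: the cross-reference in 10.2 leads to text that is not there, and nothing elsewhere gives a cohort-level trigger once the MTD is fixed. It should be repaired. General oversight already exists, so this is a gap in a prespecified rule and not an absence of safety monitoring.

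At a true rate of 35%, the dose passes on 6 patients 32% or 65% of the time, depending on which MTD criterion is used. Ten more patients at that rate would bring 3.5 expected DLTs and a 49% chance of 4 or more. These figures assume independent patients with a common DLT rate.

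A reader might also infer that 10.3 classes 35% as unacceptable. It does not: it reports an operating characteristic at that rate, and 35% is used here only for that reason. The boundary figures are an illustration. They depend on the chosen limits, on outcomes being known at once, and on which MTD criterion applies.

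**What to change.** First reconcile the two statements of the MTD criterion in 10.1: no greater than 2 DLTs in 6 under Endpoints, and at most 1 of 6 for level IV under Dose-escalation Rules. The operating characteristics of any boundary depend on which one holds, and that choice is the sponsor's.

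Then add to 10.3 a cumulative DLT boundary for the patients treated at the MTD, with limits chosen by the sponsor, under which crossing pauses accrual for DSMC review. State:

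- the look schedule;
- whether DLTs from the escalation phase count;
- how patients still inside the 30-day window are counted;
- the probability of crossing while accrual is still open, at the 20% and 35% rates already used in 10.3.

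If the sponsor intended the 2-DLT rule in 9.3 to govern the expansion, the alternative is to say so there, with an action on accrual and the same counting rules, and to correct the reference in 10.2.

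The cost is a short table and a few sentences. The downside is an occasional unneeded pause: for the illustrative limits, a 12% chance at a true rate of 20% if the MTD had at most 1 DLT in 6, and 24% if it had at most 2.

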## 10.3 Monitoring Dose-Limiting Toxicity

With 6 evaluable patients, the probability of not escalating when the true DLT rate is 35% or higher is at least 68%. If the true DLT rate is 20%, the probability that the dose will be escalated is 66%.

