## Section 10.0 Statistical considerations

### 10.1 Trial Design

This phase I trial will determine safety, dose-limiting toxicities (DLT) and maximum tolerable dose (MTD) of SRT for HCC. Although unacceptable toxicity is unlikely, four dose levels (40, 50, 60, 70 Gy in 5 fractions) will be evaluated in a cohort escalation design of 3-6 patients. At the MTD, 10 additional patients will be enrolled to generate pilot data on radiologic response and to evaluate further toxicity. Patients will start at dose level II (50 Gy at 5 fractions).

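### Section 10.3's 68% and 66% describe a fixed six-patient decision; the written rule for dose levels II and III gives 60.4% and 70.9%

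*Combined protocol and SAP*

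**What the plan says.** Section 10.3 rests on six evaluable patients and makes two statements: "the probability of not escalating when the true DLT rate is 35% or higher is at least 68"%, and "If the true DLT rate is 20%, the probability that the dose will be escalated is 66"%.

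Section 10.1 describes the trial as one whose four dose levels "will be evaluated in a cohort escalation design of 3-6 patients". Its Dose-escalation Rules set out the steps. "Three patients will initially be treated at each dose level". At level II, if none of the three has a DLT, "then the third dose level is investigated". If one of the three has a DLT, three more are entered: "If none of the additional patients develop DLT, then the third dose will be investigated". Two DLTs among the first three mean that the level has exceeded the MTD. Level III follows the same pattern.

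Level IV differs. Unless two of the first three have a DLT, the cohort is always filled to six: "If at most 1 of 6 patients develops DLT, then the fourth dose will be declared the MTD".

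Other sections state other rules. Section 9.3 stops escalation at two DLTs on a level and adds: "If one patient has a DLT, then an additional five patients will be evaluated at the same dose level". Section 5.2.2 speaks of cohorts of five. The Endpoints part of Section 10.1 defines the MTD by up to two DLTs in six.

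**The concern.** The probabilities in Section 10.3 assume that six patients are seen before the decision. At levels II and III, the only levels from which this trial can escalate after starting at level II, the written rule often decides on three. A rule that can escalate on less information has different operating characteristics, so the two figures may not belong to this design.

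They are the plan's only statement of how well the escalation protects patients, and the 68% is worded as a minimum. If the true minimum under the written rule is lower, a safety reviewer is given more reassurance than the design provides.

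**Working it through.** **Inputs.** True DLT rates of 35% and 20%, and the stated 68% and 66% (Section 10.3). First cohort of three, escalate on 0/3, add three on 1/3 and escalate only if the added three have no DLT (Section 10.1, Dose-escalation Rules). The rules do not list 3/3; it is taken as not escalating. Write p for the DLT rate and q = 1 − p.

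**1. Reproducing the plan's figures.** With six patients always observed and the dose passing on at most one DLT:

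P(pass) = q⁶ + 6pq⁵

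- p = 0.35: 0.0754 + 0.2437 = 0.3191, so 68.1% do not pass.
- p = 0.20: 0.2621 + 0.3932 = 0.6554, so 65.5% pass.

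These are the stated 68% and 66%.

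**2. The written rule at levels II and III.**

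P(escalate) = q³ + 3pq² × q³

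- p = 0.35: 0.2746 + 0.4436 × 0.2746 = 0.3965, so 60.4% do not escalate. Stated floor 68%: shortfall 7.6 points.
- p = 0.20: 0.5120 + 0.3840 × 0.5120 = 0.7086, so 70.9% escalate. Stated 66%: difference 4.9 points.

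The probability of not escalating rises with p, so the floor for rates of 35% or more is its value at 35%. It reaches 68% only at a true rate of about 39%. At 35%, 0.2746 / 0.3965 = 69% of escalations follow just three patients.

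**3. Where the gap comes from.** The two rules differ only when the first three patients have no DLT and the next three would have had two or more. The written rule escalates before seeing those next three.

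- p = 0.35: P(0/3) × P(at least 2 of 3) = 0.2746 × 0.2818 = 0.0774.
- p = 0.20: 0.5120 × 0.1040 = 0.0532.

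These equal 0.3965 − 0.3191 and 0.7086 − 0.6554, so the gap is fully explained. The expected number of patients per decision, 3 + 3 × 3pq², is 4.3 at 35% and 4.2 at 20%, not six.

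**4. Other readings of the six-patient wording.**

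| Reading | Not escalating at 35% | Escalating at 20% |
|---|---|---|
| Stated in Section 10.3 | at least 68% | 66% |
| Fixed six, at most one DLT | 68.1% | 65.5% |
| Written rule, levels II and III | 60.4% | 70.9% |
| Written rule, given that six were entered | 72.5% | 51.2% |
| Section 9.3, three patients, then five more after one DLT | 67.4% | 63.8% |
| Section 9.3, five patients, then five more after one DLT | 84.8% | 46.2% |
| Fixed six, at most two DLTs | 35.3% | 90.1% |

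Under the written rule, six are entered before the decision only after exactly 1/3: 44.4% of the time at 35% and 38.4% at 20%. Given that, the values are 1 − q³ = 72.5% and q³ = 51.2%. Level IV does give 68.1% and 65.5%, but as probabilities of not declaring and of declaring the MTD; there is no higher level to escalate to.

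**The case against.** Section 10.3 contains no calculation error. It names six evaluable patients, and on that basis both figures are right to rounding. Six per level is also the planning basis elsewhere: the 18 and 12 evaluable patients in Section 10.5 are three and two levels of six, and the MTD is defined on six. Section 9.3's clause stopping at two DLTs, applied alone to six patients enrolled outright, gives exactly the stated pair. The documents do not say which rule prevails, and one version of the Section 9.3 rule gives more protection than stated. Nothing in the conduct or analysis of the trial depends on the 68% or 66%, and escalating on 0/3 is an ordinary feature of a 3+3 design.

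Much of this stands. The fault is a mismatch between the figures and the rule, not a slip in the binomial sum, and its practical consequence is limited. The shortfall also depends on treating the Dose-escalation Rules as governing, which is reasonable because they are the detailed rule within the statistical section.

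It does not rescue the text. The six per level in Section 10.5 is a maximum, and levels II and III do not enrol six outright. Section 9.3's complete rule, with five added patients, does not give both stated figures. Nor can Section 10.3 be describing the expansion phase, for which Section 10.2 points to it: that phase enrols 10 patients and involves no escalation.

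**Conclusion.** The concern holds. The figures in Section 10.3 belong to a decision on six patients, and no escalation step in the Dose-escalation Rules is made that way. For levels II and III as written, the chance of not escalating at a 35% DLT rate is 60.4%, so the stated floor fails. A level with that rate is passed 39.6% of the time, against an implied maximum of 32%. At a 20% rate the design escalates more readily than stated, 70.9% against 66%.

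This rests on the Dose-escalation Rules governing, on 3/3 being treated as not escalating, and on independent patients with a common DLT rate at each level. Counting 3/3 any other way would lower the protection further. The error affects what the plan claims about its design, not how patients would be treated. It should be corrected, but it does not undermine the trial.

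**What to change.** First reconcile the four statements of the rule: cohorts of five in Section 5.2.2, five added patients in Section 9.3, up to two DLTs in six in the Endpoints part of Section 10.1, and the Dose-escalation Rules. Which rule governs is for the sponsor to decide. Then recompute Section 10.3 for that rule and say which dose levels each probability covers.

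If the Dose-escalation Rules stand, state for levels II and III about 60% not escalating at a 35% DLT rate and about 71% escalating at 20%. A short table would serve readers better than two points:

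| True DLT rate | 10% | 20% | 30% | 35% | 40% | 50% |
|---|---|---|---|---|---|---|
| P(escalate) | 90.6% | 70.9% | 49.4% | 39.6% | 30.9% | 17.2% |

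The same edit should state what happens after 3/3. The 68% and 66% can stay only if they are relabelled as the level IV six-patient MTD decision.

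The cost is wording and a small calculation. If the Dose-escalation Rules stand, no patients are added. The price is that the stated protection at a 35% DLT rate becomes visibly weaker, about 60% instead of 68%.

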## 10.4 Plans for Data Analysis

Toxicity will be graded and tabled by dose level. At the MTD, the rates of radiological complete and partial responses and 90% exact binomial confidence intervals will be calculated.

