## Section 1.0 Objectives

- 1.1 Primary Objective:
  - 1.1.1 The safety of hypofractionated stereotactic radiotherapy in patients with advanced hepatocellular carcinoma.
    - 1.1.1.1 Record SRT related liver, right kidney, small bowel toxicity according CTCAEv3.0
- 1.2 Secondary Objective:
  - 1.2.1 The maximum tolerable SRT dose.
  - 1.2.2 Objective tumor response rate.
    - 1.2.2.1 Report the percentage of tumor size change on CT
    - 1.2.2.2 Report the percentage of intensity change on MRI
    - 1.2.2.3 Report the percentage of change in AFP
  - 1.2.3 The value of 4D CT in liver cancer planning
    - 1.2.3.1 Report extent of liver motion three dimensionally
    - 1.2.3.2 Report the percentage of patients requiring breath gating because of the amplitude of organ motion exceeding 1 cm in any dimension.
  - 1.2.4 The value of breath gating in liver cancer SRT
    - 1.2.4.1 Report the success rate of breath gating
    - 1.2.4.2 Report the percentage of treatment time prolongation secondary to the gating.

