## **Section 3.0 Eligibility Criteria**

### **3.1 Inclusion Criteria:**

Patients must meet all the following criteria

- 3.1.1 Male or female patients  $\geq$  19 years of age
- 3.1.2 A life expectancy of at least 12 weeks with a Karnofsky performance status  $\geq$  60% (Appendix V)
- 3.1.3 Histologically or cytologically documented HCC
- 3.1.4 The target lesion can be accurately measured in at least one dimension according to RECIST and must have a maximum tumor diameter of  $\leq$  8 cm

- 3.1.5 Previous systemic chemotherapy or non-radiation local therapy (such as surgery, hepatic arterial therapy, chemoembolization, radiofrequency ablation, percutaneous ethanol injection or cryoablation) is allowed. Local therapy must be completed at least 6 weeks prior to the baseline scan.
- 3.1.6 Cirrhotic status of Child-Pugh class A and B (Appendix I)
- 3.1.7 Platelet count  $\geq 60 \times 10^9/L$ , Hemoglobin  $\geq 8.5$  g/dL, WBC  $\geq 2000/\mu L$
- 3.1.8 International normalized ratio (INR) must be  $\leq 2.3$ . Patients who are being therapeutically anticoagulated with an agent such as Coumadin or heparin will be allowed to participate provided that no prior evidence of underlying abnormality in these parameters (PT, PTT, INR) exists.
- 3.1.9 Must be aware of the neoplastic nature of his/her disease and willingly provide written, informed consent after being informed of the procedure to be followed, the experimental nature of the therapy, alternatives, potential benefits, side-effects, risks and discomforts.

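### Section 10.4 tables toxicity by grade reached with no baseline reference, so the table can mix existing liver or blood-count abnormality with SRT effect

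*Combined protocol and SAP*

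**What the plan says.** Section 10.4 deals with safety in one sentence: "Toxicity will be graded and tabled by dose level". It names no baseline value, no change from baseline and no attribution condition. The Endpoints part of Section 10.1 adds that "all toxicities observed within 1 month after SRT will be scored". The primary objective in Section 1.0 is narrower: "Record SRT related liver, right kidney, small bowel toxicity according CTCAEv3.0".

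Section 3.1.6 sets liver function at entry as "Cirrhotic status of Child-Pugh class A and B (Appendix I"). The rest of Section 3.1 caps INR at 2.3 and sets floors for platelets (60 × 10⁹/L), hemoglobin (8.5 g/dL) and WBC (2000/µL). It gives no separate limit for bilirubin, AST or ALT.

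For DLTs, Section 10.1 lists item (a), "grade 4 or 5 hepatic", and item (d), "grade 4 hepatic liver enzyme elevations persisting for" at least 5 days. Both are grades reached. The list is limited to toxicity "that is possibly, probably or definitely related to SRT occurring within 30 days from the start of treatment". Section 9.3 is wider: "Any grade 4 or greater toxicity according to CTCAE v3 will constitute a DLT", with no attribution condition. Later text in Section 9.3 treats deterioration of an existing concurrent illness as an adverse event and has a relationship recorded for every event.

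**The concern.** The background section states that more than 80% of HCC arises in cirrhotic liver, so many patients can be expected to start with abnormal liver tests, and the entry floors also allow low blood counts. If the table shows only the grade reached, a patient whose values never change and a patient injured by SRT can occupy the same cell. The purpose of a phase I safety table is comparison across dose levels. With cohorts of three to six, the number of Child-Pugh B patients can differ between levels by chance alone, and that difference could be read as a dose effect or could hide one. What is at stake is the interpretation of the primary safety result.

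**Working it through.** The plan gives no figure on this point. The probabilities in Section 10.3 concern escalation and do not depend on how the table is laid out.

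1. **Liver function at entry (Section 3.1, Appendix I).** Bilirubin above 3.0 mg/dl scores 3, the top score. With the other four items at 1, the total is 3+1+1+1+1 = 7. Class B is 7–9, so the patient is eligible, and since 3 is the maximum, a higher bilirubin adds no points. The other four items may together score up to 9 − 3 = 6. AST and ALT are not among the five items, so nothing in Section 3.1 limits them.

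2. **Blood counts at entry.** Platelets may be as low as 60 × 10⁹/L. DLT item (e) in Section 10.1 refers to recovery of thrombocytopenia to a level of 80 (no unit printed; read here as × 10⁹/L). A patient entering at 60–79 is below that level before any SRT. Section 5.5 (Dose Modifications) uses a third figure: treatment resumes above 50,000/µL. The documents' own figures thus show a fixed threshold that an eligible patient can already miss at entry.

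3. **How this reaches the table.** Assumption: CTCAE v3.0 grades laboratory values against fixed limits. Its text is not in the documents. An unchanged abnormal value then has the same grade before and after SRT:

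| Baseline grade | Worst grade after SRT | Shown by Section 10.4 | Worse than baseline? |
|---|---|---|---|
| 0 | 2 | grade 2 | yes |
| 2 | 2 | grade 2 | no |
| 2 | 3 | grade 3 | yes |

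   The first two rows cannot be told apart in the planned table. A shift table separates them.

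4. **Size per patient.** One patient with an unchanged baseline abnormality adds 1/3 = 33 percentage points to a cohort of three and 1/6 = 17 points to a cohort of six. At the maximum tolerable dose, with 6 + 10 = 16 patients, the addition is 1/16 = 6 points. The effect is largest where dose levels are compared.

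5. **Effect on hepatic DLT items (a) and (d).** Both need grade 4 or above. A patient who enters at grade 3 or lower and reaches grade 4 has worsened, so the event counts with or without a baseline reference. A patient who enters at grade 4 and dies of the event (grade 5) has also worsened. Only a patient already at grade 4 who stays there is treated differently. The documents do not say how often that occurs.

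6. **Available data.** Section 7.1 marks bilirubin, alkaline phosphatase, AST, ALT, blood counts and coagulation tests at baseline. Appendix II has chemistry and blood counts at screening, 1–7 days after marker implantation, at SRT planning, and at 1 and 3 months. Child-Pugh status is assessed at registration (Section 4.2). INR is a gap: Section 7.1 repeats it after SRT, while Appendix II lists it at screening only.

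**The case against.** The strongest reply is that the plan already filters by attribution. Section 10.1 counts a DLT only if it is at least possibly related to SRT, the primary objective is limited to SRT-related toxicity, and Section 9.3 treats deterioration of an existing illness as the adverse event, which implies a baseline. An investigator can call an unchanged value unrelated. Entry is also protected by performance status, life expectancy, the exclusion of uncontrolled illness, and confirmation of eligibility by hepatologists (Section 4.4). Finally, with at most 28 patients and baseline values on file, nothing prevents a shift table at reporting.

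Much of this stands. A reader might infer that existing cirrhotic dysfunction is scored as SRT toxicity and counted as a DLT. The documents do not support that: the Section 10.1 filter can exclude it, and items (a) and (d) need grade 4 or above. The uncapped bilirubin is a corner case, since it leaves few points for the other items.

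A reader might also put a figure on lost escalations. With an assumed true DLT rate of 10% and an assumed 20% background, the apparent rate is 1 − 0.9 × 0.8 = 28%. The Section 10.1 rule, (1−p)³ + 3p(1−p)⁵, then gives a chance of escalating of 0.536 instead of 0.906. The arithmetic is right, but the background rate is not in the documents. By step 5, a baseline rule would remove only patients already at grade 4 at entry, so the figure does not measure what the change would achieve.

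What the reply does not meet is the table itself. Section 10.4 states neither an attribution condition nor a baseline rule. The relationship item in Section 9.3 is worded for study medication, although Section 8.0 says no drugs are used. The Section 9.3 wording makes worsening an adverse event, but does not say that only worsening is graded or tabled. That a shift table could be produced later is a reason to specify it now, before results by dose are known.

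**Conclusion.** The point holds for the toxicity table. Section 10.4 summarises the grade reached, entry permits abnormal liver tests and blood counts, and the primary objective concerns SRT-related toxicity, so the table can mix existing abnormality with SRT effect, and the mix can differ between cohorts. Each affected patient moves a three-patient cohort by 33 points. The number of affected patients is unknown, so no overall bias can be stated. The conclusion assumes that CTCAE v3.0 uses fixed laboratory limits; if it graded against baseline, the laboratory part would fall away.

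For DLTs the finding is narrower. The documents do not establish that escalation is distorted. They do contain two DLT definitions, one with an attribution condition and one without, and neither says how a raised baseline grade is treated.

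**What to change.** In Section 10.4:

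- Table the worst post-SRT grade against the patient's baseline grade, by dose level, for each graded laboratory item, and show Child-Pugh class in the same display.
- Report worsening from baseline as the summary of SRT toxicity, beside the counts by grade reached.
- Define baseline, since Appendix II has three pre-SRT laboratory times, and state the window for the worst grade. Section 10.1 uses one month after SRT for scoring and 30 days from the start of treatment for DLTs.
- Align Section 7.1 and Appendix II on INR if it is to be included.

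For DLTs, no new rule is proposed here, because the definition governs escalation (Section 10.1) and removal from study (Section 5.6.3). The sponsor should reconcile the Section 9.3 definition with that in Section 10.1 and with the worsening wording in Section 9.3. The sponsor should also state how baseline grade is handled, and reconcile the platelet figures of 60, 80 and 50 in Sections 3.1.7, 10.1(e) and 5.5.

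The cost is a few sentences of analysis text; no new patients are needed, and no new tests for bilirubin, AST, ALT or blood counts. One small downside is that a patient who enters at a high grade has less room to worsen and contributes less to that item, but the shift table makes this visible.
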